### Safety Analysis

All patients will be considered evaluable for safety after the first dose of therapy. AEs and clinically significant laboratory abnormalities with associated incidence rates and severities will be tabulated.

#### Deaths and Serious Adverse Events

Serious adverse events and deaths will be listed. Data from the adverse event page that specify the event is serious will be used to generate the listing.

Summaries of serious unique adverse events will include:

- all serious treatment emergent adverse events,
- all serious treatment emergent adverse events by sex,
- all serious treatment emergent adverse events by race,
- all serious treatment emergent adverse events by the worst grade,
- all related serious treatment emergent adverse events by the worst grade.

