### 3.3.1.3 Liver Chemistry Stopping and Follow-up Criteria

#### 3.3.1.3.1 Liver Chemistry Stopping Criteria

3.3.1.3.1.1 Liver chemistry stopping and follow up criteria have been designed to assure subject safety and evaluate liver event etiology. All subjects who meet liver chemistry criteria requiring permanent discontinuation of lapatinib must continue to be followed for the study assessments and procedures as defined in Section 3.7.6 and Appendix 12.5. If a subject experiences  $ALT > 3 \times ULN$  and total bilirubin  $> 2.0 \times ULN$  ( $> 35\%$  direct; bilirubin fractionation required\*), then the following actions must be taken:

- immediately and permanently discontinue investigational product;
- complete the SAE data collection tool, and the clinical evaluation CRF;
- in addition to the liver event follow up assessments defined below, the following are suggested: specialist or hepatology consultation; anti-nuclear antibody, anti-smooth muscle antibody, and Type 1 anti-liver kidney microsomal antibodies; and liver imaging and/or liver biopsy to evaluate liver disease;
- promptly report the event to NCI CCR within 24 hours of learning of its occurrence (refer to Section 7.4);
- monitor every week until liver chemistries resolve, stabilize or return to within baseline values;
- do not re-challenge with lapatinib.
- **NOTE:** bilirubin fractionation should be performed if testing is available. If testing is unavailable and a subject meets the criterion of total bilirubin  $> 2.0 \times ULN$ , then the aforementioned actions must still be performed.

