- In addition, any subject who develops clinical signs and symptoms of cardiac failure should undergo an LVEF assessment and ECG.

3.7.8 After enrollment on the clinical trial, patients will complete as baseline measures the MDASI-BT or MDASI-SP. The patient will continue to complete the MDASI-BT and/or MDASI-SP at the time of clinical evaluation with MRI as long as the clinical therapy is being administered, unless clinical deterioration makes self-report not possible before that time. The time when patients are unable to complete the self report questionnaires will be used as part of the study analysis. The MDASI-BT and/or MDASI-SP will be completed only by the patient, unless changes in vision or weakness make this difficult. If this occurs, then the caregiver or research assistant may read the questions to the patient or assist with marking the severity number or score as described by the patient. A patient caregiver may complete the questionnaires as a patient-preference proxy if the patient’s deficits preclude self report.

3.7.9 Off treatment follow-up will continue on the following schedule until the patient meets off study criteria.

3.7.9.1 For patients with stable disease or response, MRI surveillance should continue every 2 months for 1 year after treatment completion, then every 3 months for 1 year, then every 4 months for 1 year, then every 6 months until progressive disease is noted, death or lost to follow-up.

3.7.9.2 Patients removed from study treatment for disease progression or treatment-related toxicity should continue to be followed with quarterly (every 3 month) updates of treatment regimens, disease status and survival.

3.7.9.3 Stable disease (SD) patients who develops progression while being followed on the “off treatment follow-up schedule”, will continue with follow-up requirements on the PD off treatment follow-up schedule, until patient meets off study criteria.

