## **7.2 GENERAL DEFINITIONS**

### **7.2.1 Adverse Event**

An adverse event is defined as any reaction, side effect, or untoward event that occurs during the course of the clinical trial associated with the use of a drug in humans, whether or not the event is considered related to the treatment or clinically significant. For this study, AEs will include events reported by the patient, as well as clinically significant abnormal findings on physical examination or laboratory evaluation. A new illness, symptom, sign or clinically significant laboratory abnormality or worsening of a pre-existing condition or abnormality is considered an AE. All AEs must be recorded on the AE case report form.

All AEs, including clinically significant abnormal findings on laboratory evaluations, regardless of severity, will be followed until return to baseline or stabilization of event. Serious adverse events that occur more than 30 days after the last administration of investigational agent/intervention and have an attribution of at least possibly related to the agent/intervention should be recorded and reported as per section 7.4

An abnormal laboratory value will be considered an AE if the laboratory abnormality is characterized by any of the following:

- Results in discontinuation from the study
- Is associated with clinical signs or symptoms
- Requires treatment or any other therapeutic intervention

- Is associated with death or another serious adverse event, including hospitalization.
- Is judged by the Investigator to be of significant clinical impact
- If any abnormal laboratory result is considered clinically significant, the investigator will provide details about the action taken with respect to the test drug and about the patient's outcome.

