#### 7.4.2 NCI-IRB Requirements for PI Reporting at Continuing Review

The protocol PI will report to the NCI-IRB:

1. A summary of all protocol deviations in a tabular format to include the date the deviation occurred, a brief description of the deviation and any corrective action.
2. A summary of any instances of non-compliance
3. A tabular summary of the following adverse events:
  - All Grade 2 **unexpected** events that are possibly, probably or definitely related to the research;
  - All Grade 3 and 4 events that are possibly, probably or definitely related to the research;
  - All Grade 5 events regardless of attribution;
  - All Serious Events regardless of attribution.

**NOTE:** Grade 1 events are not required to be reported.

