### 7.5 NCI GUIDANCE FOR REPORTING EXPEDITED ADVERSE EVENTS FOR MULTI-CENTER TRIALS

The site PI must immediately report to the coordinating center PI any serious adverse event, whether or not considered drug related, including those listed in the protocol or investigator brochure and must include an assessment of whether there is a reasonable possibility that the drug caused the event within 24 hours of PI awareness of the event. The Site PI must also report any protocol deviations to the coordinating center PI within 7 days of PI awareness. Participating centers must also submit the report to their IRB in accordance with their institutional policies.

Participating centers must also submit the report to their IRB in accordance with their institutional policies. The CCR problem report form will be used for this purpose (Appendix [12.9](#)).

Occasionally NCI IRB or the PI may contact the reporter for additional information, clarification, or current status of the subject for whom an adverse event was reported.

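### The Section 8 deaths listing is drawn only from adverse event pages marked serious, so late deaths attributed to tumor or called unrelated can be missing from it

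*Combined protocol and SAP*

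**What the plan says.** Under Deaths and Serious Adverse Events, Section 8 states: "Serious adverse events and deaths will be listed". It sets no time limit on either. The only source it names follows directly: "Data from the adverse event page that specify the event is serious will be used to generate the listing".

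What reaches that page is governed by Section 7.2.1. It defines an adverse event as, among other things, an "untoward event that occurs during the course of the clinical trial", whether or not related to treatment, and requires all adverse events to go on the case report form. It then treats a late group separately: serious events that arise beyond 30 days from the last dose and "have an attribution of at least possibly related to the agent/intervention should be recorded and reported as per section 7.4".

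After treatment, Section 3.7.9.2 says that patients taken off for progression or treatment-related toxicity "should continue to be followed with quarterly (every 3 month) updates of treatment regimens, disease status and survival". Adverse events are not among the items named. Section 6.2.7 defines survival by death from any cause.

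**The concern.** The listing and the follow-up record read from different forms. A death several months after the last dose is picked up by the quarterly survival update. It enters the Section 8 listing only if someone also completes an adverse event page for it and marks it serious, and 7.2.1 can be read as asking for that only when the investigator considers the event at least possibly related.

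For late deaths, inclusion would then depend on the attribution that a complete listing should let a reader check. This is a single-arm trial, so no control group shows what to expect. The protocol itself names temozolomide risks that could plausibly surface after treatment ends: myelodysplastic syndrome and new cancers including myeloid leukemia (10.1.9 and the rare-but-serious list after it). No efficacy result is at stake. What is at stake is whether the deaths listing is complete.

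**Working it through.** The plan states no figure on this point, so there is nothing to reproduce. The check sets the sections side by side and then adds an illustration of scale.

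**Step 1. The source of the listing.** Section 8 names the adverse event page and nothing else. The summaries beneath the listing are confined to treatment-emergent events, a term the plan does not define, so they do not supply a recording window either.

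**Step 2. Whether a late unrelated death must be on an adverse event page.** Section 7.2.1 does not say that recording stops at 30 days. But its sentence on late events carries two conditions: more than 30 days, and at least possibly related. If every late serious event had to be recorded anyway, the relatedness condition would do nothing for recording. Two other safety windows in the document also run to 30 days: the worst laboratory values (Section 8, Laboratory Tests) and liver abnormalities after treatment (3.7.6). A limit for unrelated events is therefore implied, not written.

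**Step 3. Where late deaths are otherwise seen.**

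| Route | What it takes | Feeds the Section 8 listing? |
|---|---|---|
| 3.7.9.2 quarterly updates | Survival | Not named as a source |
| 7.4.1 report within 7 days | Deaths other than from progression | Not named as a source |
| 7.4.2 continuing review | Grade 5 events, and "All Serious Events regardless of attribution" | Not named as a source |
| 7.5 site report within 24 hours | Serious events, related or not | Only if also entered on the adverse event page |

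So the trial learns of these deaths, but the listing as specified need not show them.

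**Step 4. Scale, as illustration only.** Assume exponential survival from the last dose with median m months and follow-up to death. Thirty days is 30/30.4375 = 0.986 months. The share of deaths beyond 30 days is 0.5^(0.986/m).

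| Assumed median m (months) | Share beyond 30 days | If all 50 patients died |
|---|---|---|
| 3 | 79.6% | 39.8 |
| 6 | 89.2% | 44.6 |
| 12 | 94.5% | 47.2 |
| 24 | 97.2% | 48.6 |

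The 50 is the maximum sample size in Section 8; the medians are assumptions. The share is an upper bound on what is omitted, because deaths called possibly related would still be recorded. An earlier data cut-off would lower it.

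**Step 5. The references to Section 7.4.** Section 7.2.1 sends late related serious events to 7.4. The 7-day list in 7.4.1 covers non-progression deaths, deviations, unanticipated problems and non-compliance; serious events as a class appear only in the continuing-review table of 7.4.2. The liver rule in 3.3.1.3.1.1 sets a 24-hour report and also refers to 7.4, which has no 24-hour rule. The 24-hour duties are in 7.5 (site to coordinating center) and 7.6 (to the manufacturer).

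**The case against.** The strongest reply is that 7.2.1 never closes the adverse event page. It defines adverse events over the course of the trial regardless of relatedness, and the 30-day sentence may only add a duty for late related events. Section 7.4.2 asks for Grade 5 events whatever their attribution, which sits badly with recording fatal events only when related. On that reading a late death belongs on the page and the listing is complete. This stands as a possible reading, and it is why the omission is a risk and not a certainty. It does not remove the problem: the window is unstated, sites can read it either way, and off-treatment follow-up does not ask for adverse events.

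A second reply is that most omitted deaths would be tumor deaths, which say little about drug safety and are already counted in survival. That is fair, and it limits the importance of the point. It does not excuse a deaths listing that leaves deaths out.

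A reader might go further and infer that late drug-related serious events are lost, or that they wait for continuing review because 7.4 gives them no deadline. The documents do not support this. Section 7.2.1 requires such events to be both recorded and reported. Section 7.5 requires a site to report "any serious adverse event, whether or not considered drug related" within 24 hours, with no limit on time since the last dose. Section 7.6 sets 24 hours to the manufacturer for all serious events and has the coordinating center forward all such reports to the IRB. The liver rule gives its own deadline and recipient, and 7.1.2 makes the combined ALT and bilirubin event reportable as serious, so 7.5 applies to it as well. What remains is a cross-reference mismatch, not a missing deadline.

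**Conclusion.** The point holds for the listing. Followed as written, Section 8 can produce a deaths listing without late deaths that were attributed to tumor or called unrelated, although survival follow-up has them. This rests on two things: the adverse event page is the only source named, which is explicit, and late unrelated events need not be recorded on it, which 7.2.1 implies but does not state. The 89% to 97% range (80% at a 3-month median) depends on assumed survival and on sites applying the implied window; it is not an estimate for this trial.

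The deaths are not lost to the trial, and efficacy results are unaffected. The references to 7.4 are a minor, separate inconsistency.

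**What to change.** 1. In Section 8, replace the source sentence with wording such as: *All deaths from registration to data cut-off will be listed from the survival and off-study records together with the adverse event pages, with cause of death and days since the last dose of each drug. Serious adverse events will be listed from the adverse event page.*
2. In 7.2.1, state the recording window outright: until when all adverse events are recorded, what is recorded after that, and which last dose starts the clock, since single-agent lapatinib may continue after protocol therapy (3.8.4.1).
3. Minor: in 7.2.1 and 3.3.1.3.1.1, add references to 7.5 and 7.6 and keep 7.4. Replacing 7.4 would drop the link to IRB and Clinical Director reporting.

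The cost is mostly wording. Survival status is already collected. Cause of death is not among the items named in 3.7.9.2, so the sponsor should confirm that it is recorded. The two sources will need reconciling where both hold the same death. The downside is a longer listing that includes tumor deaths; the cause column lets a reader separate them.

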#### Neurological Symptoms and Signs

Neurological symptoms and signs collected on the neurological examination CRFs will be summarized at the baseline and by scheduled visit.

#### Laboratory Tests

Changes from baseline in laboratory measurements will be summarized by study visit.

The worst post-baseline laboratory measurements up to (1) 30 days after the permanent discontinuation of the study medication or (2) the initiation of subsequent anti-ependymoma therapy will be summarized. Marked laboratory toxicity (baseline grade 0 to post-baseline grade 3 or 4, or baseline grade 1 to post-baseline grade 4) will also be summarized.

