## **2 ELIGIBILITY ASSESSMENT AND ENROLLMENT**

### **2.1 ELIGIBILITY CRITERIA**

#### **2.1.1 Inclusion Criteria**

- 2.1.1.1** Histologically proven ependymoma or anaplastic ependymoma. There must be pathologic or imaging confirmation of tumor progression or regrowth. The patient's histologic diagnosis must be confirmed on Central Pathology Review prior to registration Step 2.
- 2.1.1.2** The patient must have at least 1 block of tissue available or 15 unstained slides at a minimum, for central pathology review and molecular profiling of the tissue sample.
- 2.1.1.3** History and physical examination, including neurologic examination, within 2 weeks prior to registration.

- 2.1.1.4** Patients must be able to undergo brain or spine MRI scans with intravenous gadolinium, based on tumor location(s) within 14 days prior to registration.
- 2.1.1.5** Patients must be on a steroid dose that has been stable or decreasing for at least 5 days. If the steroid dose is increased between the date of imaging and registration, a new baseline MRI is required.
- 2.1.1.6** Karnofsky performance status  $\geq 70$
- 2.1.1.7** Age  $\geq 18$
- 2.1.1.8** CBC/differential obtained within 14 days prior to registration, with adequate bone marrow function defined as follows:
  - Absolute neutrophil count (ANC)  $\geq 1,500/\text{mm}^3$
  - Platelets  $\geq 100,000 \text{ cells/mm}^3$
  - Hemoglobin  $\geq 10.0 \text{ gm/dL}$  (Note: The use of transfusion or other intervention to achieve Hgb  $\geq 10.0$  is acceptable)
  - White blood cell count (WBC)  $\geq 3,000/\text{mcL}$
  - Adequate liver function within 14 days prior to registration, defined as follows: SGPT (ALT)  $< 2.5$  times the upper limit of normal, Bilirubin  $\leq 1.6 \text{ mg/dL}$
  - Adequate renal function within 14 days prior to registration, defined as follows: Creatinine  $< 1.7 \text{ mg/dL}$
- 2.1.1.9** Patients must have recovered from the toxic effects of prior therapy, and there must be a minimum time of:
  - 28 days from the administration of any investigational agent
  - 28 days from administration of prior cytotoxic therapy with the following exceptions:
    - 14 days from administration of vincristine
    - 42 days from administration of nitrosoureas
    - 21 days from administration of procarbazine
    - 7 days from administration of non-cytotoxic agents [e.g., interferon, tamoxifen, thalidomide, cis-retinoic acid, etc. (radiosensitizer does not count)].

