#### 6.1.3 Safety Data

All patients receiving study agents will be evaluated for safety. The safety parameters include all laboratory tests and hematological abnormalities, CNS observations, physical examination findings, and spontaneous reports of adverse events reported to the investigator by patients. All toxicities encountered during the study will be evaluated according to the NCI Common Terminology Criteria for Adverse Events (CTCAE) version 4.0 and recorded prior to each course of therapy. Life-threatening toxicities that are unexpected and assessed to be possibly related to the study agent/s should be reported immediately to the study Coordinator and Institutional Review Board (IRB).

Information about all adverse events, whether volunteered by the subject, discovered by investigator questioning, or detected through physical examination, laboratory test or other means, will be collected and recorded on the Adverse Event Case Report Form and followed as appropriate. An adverse event is any undesirable sign, symptom or medical condition occurring

after starting study drug (or therapy) even if the event is not considered to be related to study drug.

Medical conditions/diseases present before starting study treatment are only considered adverse events if they worsen after starting study treatment (any procedures specified in the protocol). Adverse events occurring before starting study treatment but after signing the informed consent form are recorded on the Baseline Evaluations Adverse Events Case Report Form. Abnormal laboratory values or test results constitute adverse events only if they induce clinical signs or symptoms or require therapy, and are also recorded on the Adverse Events Case Report Form.

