### **6.3 TOXICITY CRITERIA**

The following adverse event management guidelines are intended to ensure the safety of each patient while on the study. The descriptions and grading scales found in the revised NCI Common Terminology Criteria for Adverse Events (CTCAE) version 4.0 will be utilized for AE reporting. All appropriate treatment areas should have access to a copy of the CTCAE version 4.0. A copy of the CTCAE version 4.0 can be downloaded from the CTEP web site ([http://ctep.cancer.gov/protocolDevelopment/electronic\\_applications/ctc.htm#ctc\\_40](http://ctep.cancer.gov/protocolDevelopment/electronic_applications/ctc.htm#ctc_40)).

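### The marked laboratory toxicity summary counts only rises of three or more grades, so a patient who enters with an abnormal value and worsens to grade 3 is left out of the one laboratory summary defined by grade

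*Combined protocol and SAP*

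**What the plan says.** Section 8, Laboratory Tests, plans three summaries.

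- Change over time: "Changes from baseline in laboratory measurements will be summarized by study visit".
- Worst value: "The worst post-baseline laboratory measurements up to (1) 30 days after the permanent discontinuation of the study medication", or up to the start of a later anti-ependymoma therapy.
- In addition, marked laboratory toxicity, defined as "baseline grade 0 to post-baseline grade 3 or 4, or baseline grade 1 to post-baseline grade 4".

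Only the third is defined by grade. The scale is set in Section 6.3: "CTCAE) version 4.0 will be utilized for AE reporting". No other section widens the definition of marked toxicity.

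Three provisions let patients enter with abnormal values.

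- Section 2.1.1.8 introduces the liver criterion with "Adequate liver function within 14 days prior to registration, defined as follows: SGPT (ALT" and puts the ALT limit below 2.5 times the upper limit of normal (ULN), so a raised ALT is allowed.
- The same section sets a hemoglobin floor of 10.0 g/dL, with a note that begins "The use of transfusion or other intervention to achieve Hgb" and accepts that route.
- Section 2.2.1 lists albumin, calcium, phosphorus, glucose, alkaline phosphatase and other chemistries as baseline tests that do not affect eligibility. They carry no entry limit.

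Two passages determine what else would be tabulated. Section 8, Safety Analysis, says "AEs and clinically significant laboratory abnormalities with associated incidence rates and severities will be tabulated". Section 6.1.3 says "Abnormal laboratory values or test results constitute adverse events only if they induce clinical signs or symptoms or require therapy".

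**The concern.** The definition is tied to the baseline grade in a way that excludes some patients from part of the count. Someone who enters a test at grade 1 can be counted only on reaching grade 4. Someone who enters at grade 2 or 3 can never be counted. Patients whose values are already abnormal at entry are thus the ones whose worsening to grade 3 this summary cannot show.

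What is at stake is descriptive. Section 1.1.2.2 makes the adverse event profile and tolerability of the combination a secondary objective, and Section 10.2.21 says a causal link between lapatinib and hepatobiliary disorders cannot be excluded. A reader of the results would reasonably look to the graded laboratory summary for severe worsening and would not see these patients there.

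**Working it through.** The plan gives no sample-size, power or event figure for this point, so the check is an enumeration followed by a comparison of outputs.

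**Step 1: which shifts count.** A worsening to grade 3 or 4 needs a post-baseline grade of 3 or 4 that is higher than the baseline grade. Baseline grades 0, 1 and 2 each give two such shifts and baseline grade 3 gives one: 2 + 2 + 2 + 1 = 7.

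| Shift | Rise in grades | Counted as marked |
|---|---|---|
| 0 to 3 | 3 − 0 = 3 | yes |
| 0 to 4 | 4 − 0 = 4 | yes |
| 1 to 4 | 4 − 1 = 3 | yes |
| 1 to 3 | 3 − 1 = 2 | no |
| 2 to 4 | 4 − 2 = 2 | no |
| 2 to 3 | 3 − 2 = 1 | no |
| 3 to 4 | 4 − 3 = 1 | no |

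Three shifts are counted and 7 − 3 = 4 are not. The counted shifts are exactly those with a rise of at least 3. A threshold of at least 2 grades would count five; any worsening to grade 3 or 4 would count all seven. These are counts of table cells, not of patients.

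**Step 2: can the uncounted cells be filled?** For 1 to 3, an entry value that is abnormal but eligible is needed. ALT above ULN and below 2.5 times ULN is such a value, on the assumption that a value above ULN grades as at least 1. The documents name CTCAE but do not reproduce its cut-offs. For 2 to 3, a grade 2 baseline is needed. The documents do not show that the tests with an entry limit allow this, but the Section 2.2.1 chemistries have no limit that would prevent it.

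**Step 3: would these patients appear elsewhere by grade?**

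- Change by visit has no baseline restriction, but it summarizes the size of changes and does not count patients by grade.
- Worst post-baseline value has no baseline restriction, but it is not stated to be by grade or set against baseline.
- The Safety Analysis tabulation includes severity, but it covers adverse events and clinically significant laboratory abnormalities, and Section 8 does not define the latter term.
- Under Section 6.1.3, an asymptomatic, untreated laboratory value is not an adverse event. Section 7.2.1 is broader: it adds, among others, values that lead to discontinuation and values the investigator judges to have significant clinical impact. Entry by that route depends on judgment.
- Section 7.1.2 requires reporting of all grade 4 laboratory abnormalities. This picks up 2 to 4 and 3 to 4, but not grade 3.
- The continuing-review table in Section 7.4.2 takes in non-serious grade 3 events only when they are considered related.

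**Result.** The 2 to 4 and 3 to 4 shifts are captured through grade 4 reporting. The shifts with no assured graded count are 1 to 3 and 2 to 3, when the worsening causes no symptoms, needs no treatment and is not judged clinically significant.

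**The case against.** The strongest reply is that nothing here is wrong. A rise of at least three grades is a consistent meaning for marked, and counting a one-grade change such as 2 to 3 under that name would empty the word. The summary is also an addition to two others that ignore baseline grade, and Safety Analysis names clinically significant laboratory abnormalities separately from adverse events, so the narrow rule in Section 6.1.3 need not remove them. For the liver, Section 3.3.1.3 sets follow-up at absolute ALT and bilirubin levels whatever the baseline.

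Much of this stands. The definition is coherent and may be deliberate, although the plan gives no rationale. It should be kept, and any wider count should be reported beside it under another name. What does not follow is that the cover is complete. The separate wording in Safety Analysis helps only if an asymptomatic grade 3 value is judged clinically significant.

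Three stronger readings are tempting, and the documents do not support them.

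- A reader might infer that the trial's safety analysis as a whole undercounts severe laboratory toxicity. The omission is in one summary; the partial cover is listed above.
- Because liver and marrow values govern dosing, a reader might infer that dose decisions are affected. The rules in Sections 3.3.1.3 and 3.3.2 use observed values and adverse event grades directly, and none refers to this summary.
- A reader might assume that 20% to 40% of the maximum 50 patients enter at grade 1 in a given test and conclude that 10 to 20 (0.20 × 50 to 0.40 × 50) are missed. The documents give no baseline grade frequencies. The result would in any case be the number who could not be counted for a grade 3 event, not the number of events missed.

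**Conclusion.** The point holds in a narrow form. Among the Laboratory Tests summaries, the only one defined by grade leaves out worsening from grade 1 to 3, and from grade 2 to 3 where a test has no entry limit. If such a worsening is asymptomatic and untreated, the plan does not ensure that it appears in any graded count.

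This rests on two assumptions: that some eligible abnormal entry values grade as at least 1, and that the worst-value summary is presented as measurements rather than grades. If it is presented by grade, the grade 3 values would be visible and only the link to baseline would be missing.

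The number of patients affected cannot be computed from the documents and may be small. The primary endpoint, the early stopping rule and its operating characteristics are untouched. This is a worthwhile, low-priority improvement to a descriptive safety summary.

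**What to change.** Keep the marked toxicity count as defined, and state that it means a rise of at least three grades. For each laboratory test that CTCAE version 4.0 grades, add a shift table of baseline grade by worst post-baseline grade, using the observation window already set for the worst value. Beneath it, report the number of patients with any worsening to grade 3 or 4. The existing count is a subset of this table, so nothing is lost.

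The table uses results already collected under Sections 3.6 and 3.7, so closed accrual (Section 2.3) is no obstacle. The cost is one more table per test and possibly higher reported counts of severe laboratory worsening than the current definition would give.
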